3.2.2.2.5 Down Titration Period

Down-Titration Period will start after the Evaluation Period or after the BRV Extension Period, can last up to 1 week. The end of the Down-Titration period is defined as day and time of last BRV administration.

3.2.2.6 Safety Follow-Up Period

Subjects will proceed to the Safety Follow-Up Period once they complete the Down-Titration Period. The end of the Safety Follow-up Period will be defined as last contact to the subject, which will be the Follow-Up visit. This visit will occur 30 ± 3 days after the final administration of BRV.

3.2.3 Mapping of assessments performed at Early Discontinuation Visit

Efficacy and safety assessments at an Early Discontinuation Visit (EDV) that corresponds to a scheduled visit will be summarized at the scheduled visit corresponding to the EDV if the assessment was scheduled to occur at that visit. Such assessments will also be considered for Last Value. In particular, vital signs, body weight, heart rate monitoring, laboratory parameters, PK samples and VEEG assessments are done at different time points of the Evaluation Period. All assessments of these variables at EDVs corresponding to a scheduled visit will be mapped to the corresponding scheduled visit.

3.2.4 Definition of completed study

Subjects will be classified as completed the study if they complete the Safety Follow-up Visit or if they complete the Extension Period Visit 2 (EPV2) and continue BRV treatment in the Follow-up study.

3.3 Postnatal age (PNA), Gestational age (GA) and Corrected Gestational age (CGA)

PNA at the time of enrollment or the time elapsed after birth in days will be calculated as the date of signed informed consent minus the date of birth.

GA will be calculated in weeks using PNA in weeks and CGA in weeks with the following formula:

$$GA = CGA - PNA$$

PNA in weeks will be calculated as PNA in days divided by 7 and rounded up to the nearest week. The PNA in weeks for subjects 7 days old and younger will be one week, for subjects aged more than 7 days old and less than or equal 14 days will be two weeks and so on.

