6 SELECTION AND WITHDRAWAL OF SUBJECTS

6.1 Inclusion criteria

To be eligible to participate in this study, all of the following criteria must be met:

1. An Independent Ethics Committee (IEC)-approved written ICF is signed and dated by the parent(s) or legal representative(s).
- 2a. Confirmation on VEEG of ≥ 2 minutes of cumulative ENS or ≥ 3 identifiable ENS prior to entering the Evaluation Period (ENS is defined as a seizure lasting for at least 10 seconds on VEEG), despite receiving previous AED treatment for the treatment of electroencephalographic seizures.

The occurrence of ENS during an up to 1-hour period must be confirmed either by the local or central VEEG reader prior to drug administration. Preferably, the central VEEG reader should confirm the required ENS.

3. Subject is male or female and must be at least 34 weeks of CGA. In addition, term neonates up to 27 days of PNA and preterm neonates up to 40 weeks of CGA and 27 days of PNA can be enrolled.
4. Subject weighs at least 2.3kg at the time of enrollment.
5. Subjects with or without concomitant hypothermia treatment.

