6 DEMOGRAPHICS AND OTHER BASELINE CHARACTERISTICS

6.1 Demographics

Demographic summaries will be presented for the FAS, PK-PPS and SS overall and by cohorts. The variables to be considered are:

- Corrected gestational age
- Postnatal age (as defined in [Section 3.3](#))
- Gestational age (as defined in [Section 3.3](#))
- Gestational age category (Pre-term <37 weeks vs Full term \geq 37 weeks)
- Gender
- Weight (g)
- Length (cm)
- Head circumference (cm)
- Racial group (American Indian/Alaskan Native, Asian, Black, Native Hawaiian or Other Pacific Islander, White, and Other/Mixed)
- Country
- Apgar score (1 minute)

- Apgar score (5 minutes)
- HIE status

The listing of demographics including Apgar score will be provided for all subjects screened.

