12.2.4 Chemistry (Bilirubin)

Bilirubin mg/dl			
Postnatal Age	GA<38	GA≥38	Comment
≤12 h	6	8	Considered PCST if bilirubin values reach cutoff for phototherapy recommendation, considering neonates with risk factors Based on AAP guideline 2004 ⁶
>12 h and ≤ 24 h	8	10	
>24 h and ≤ 48 h	11	13	
>48 h and ≤ 72 h	13	15	
>72 h and ≤ 96 h	14	17	
> 96h	15	18	

⁶ Management of Hyperbilirubinemia in the Newborn Infant 35 or More Weeks of Gestation, AAP, PEDIATRICS Vol. 114 No. 1 July 2004

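### SAP 3.3 derives gestational age by subtracting postnatal age rounded up to whole weeks, with no rounding rule for corrected gestational age, so babies born in week 37 can be reported as preterm.

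*SAP*

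**What the plan says.** SAP 3.3 defines three ages. PNA in days "will be calculated as the date of signed informed consent minus the date of birth", so a baby consented on the day of birth has PNA 0. For GA, "GA will be calculated in weeks using PNA in weeks and CGA in weeks with the following formula": GA = CGA - PNA. The conversion of PNA is then fixed: "PNA in weeks will be calculated as PNA in days divided by 7 and rounded up to the nearest week". An illustration follows: one week for babies aged 7 days or less, two weeks for those over 7 and up to 14 days, and so on. Nothing is said about whether CGA in weeks is exact, truncated or rounded.

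SAP 6.1 carries the result into the demographic tables for the FAS, PK-PPS and SS. It lists "Gestational age (as defined in" Section 3.3 and, next to it, "Gestational age category (Pre-term <37 weeks vs Full term" at 37 weeks or more.

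SAP 12.2.4 also uses GA. It sets the bilirubin limits for possibly clinically significant values in two columns, GA below 38 weeks and GA of 38 weeks or more, with the comment "Considered PCST if bilirubin values reach cutoff for phototherapy recommendation". It does not say where that GA comes from.

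**The concern.** GA at birth is a fixed quantity. It equals CGA at enrollment minus the time elapsed since birth, with both measured on the same scale. Rounding only the elapsed time, and always upward, removes more than has elapsed. A baby consented on its day of birth has GA equal to CGA, yet the SAP would record GA as CGA minus one week.

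The rule also disagrees with its own illustration at that point: 0/7 rounded up is 0, while the illustration assigns 1.

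At stake is a baseline table that describes the maturity of a small neonatal population. With 12 subjects per Confirmatory Cohort, one misplaced baby moves a cohort's preterm percentage by 1/12, or about 8 points. If the same GA selects the bilirubin column, some safety flags would be raised against the wrong limit.

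**Working it through.** **Inputs.** GA = CGA - PNA weeks, and the PNA bands, from SAP 3.3. PNA 0 to 27 days at enrollment, from Protocol 6.1: "term neonates up to 27 days of PNA and preterm neonates up to 40 weeks of CGA and 27 days of PNA can be enrolled". The 37-week cut from SAP 6.1 and the 38-week cut from SAP 12.2.4. CGA rounding is not given, so four conventions are shown.

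**Reproducing the plan's bands.** Let d be PNA in days and W(d) the PNA in weeks. Take W = 1 for d of 0 to 7, and otherwise d/7 rounded up. This gives 1 week through day 7, 2 weeks for days 8 to 14, 3 for days 15 to 21 and 4 for days 22 to 27, matching the illustration.

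**Size of the error with exact CGA.** Understatement = W(d) - d/7.

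- d = 0: 1 - 0 = 1.00 week
- d = 1: 1 - 1/7 = 0.86
- d = 2: 1 - 2/7 = 0.71
- d = 3: 1 - 3/7 = 0.57
- d = 7, 14, 21: 0
- d = 8: 2 - 8/7 = 0.86, then falling again to 0 at day 14, and so on

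The unweighted mean is 0.57 week over days 0 to 6 and 0.46 over days 0 to 27.

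**Example.** A baby born at 37w0d and enrolled on day 2 has CGA 37w2d = 37.29 weeks. Derived GA = 37.29 - 1 = 36.29, or 36 if CGA is in completed weeks. The baby is listed as preterm.

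**Crossing the 37-week cut.** Take true GA 37 weeks plus a days, with a from 0 to 6. With exact CGA, derived GA is below 37 when a < 7W(d) - d. The number of values of a that satisfy this is 7, 6, 5, 4, 3, 2, 1 for d = 0 to 6, a total of 28 out of 7 × 7 = 49. It is 0 at days 7, 14 and 21. Each of the runs 8-13, 15-20 and 22-27 adds 6+5+4+3+2+1 = 21. The total is 28 + 3 × 21 = 91 out of 7 × 28 = 196. Completed-week CGA gives the same counts, because the whole-week part of (a + d) falls below W(d) under the same condition. Its largest shortfall against exact GA is 1 + 6/7 = 1.86 weeks.

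**Sensitivity to the unstated CGA convention.**

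| CGA used as | Error in GA (weeks) | Week-37 births called preterm (of 196) | of which PNA 0-6 (of 49) | Week-36 births called term (of 196) |
|---|---|---|---|---|
| Exact | -1.00 to 0 | 91 | 28 | 0 |
| Completed weeks | -1.86 to 0 | 91 | 28 | 0 |
| Nearest week | -1.43 to +0.43 | 28 | 10 | 21 |
| Rounded up | -1.00 to +0.86 | 1 | 1 | 78 |

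Under all four conventions no birth at 38w0d or later is called preterm.

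If the rounding sentence rather than the illustration governs at PNA 0, W(0) = 0. The 7 day-0 combinations then drop out of the first two rows: 28 - 7 = 21 of 49 and 91 - 7 = 84 of 196.

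**Bilirubin columns.** The same algebra holds with 38 in place of 37. The paired limits in SAP 12.2.4 (GA below 38 / 38 or more) are 6/8, 8/10, 11/13, 13/15, 14/17 and 15/18 mg/dL. They differ by 2 up to 72 hours and by 3 after that.

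**The case against.** The strongest reply is that size and direction rest on an input the SAP does not give. If CGA were rounded up in the same way as PNA, the mean error would be only -0.04 week, and the main misclassification would be preterm to term. That stands as a limit on any one figure. It does not rescue the rule, since each of the four conventions puts some combinations on the wrong side of 37 weeks.

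A reader might infer several stronger things that the documents do not support.

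- **That GA is always understated, by at most a week.** This holds only for exact CGA. The range differs for each of the other conventions.
- **That term babies in general are called preterm, or that many subjects are affected.** Only week-37 births can cross that cut downward. The documents give no distribution of GA or enrollment age, so the combination counts are not a forecast of subjects.
- **That the bilirubin flags are wrong.** SAP 12.2.4 neither cites 3.3 nor names a GA source, and it uses postnatal age in hours, which 3.3 does not derive. The consequence is conditional.
- **That efficacy or eligibility is touched.** The responder definition (SAP 8.1.1), the efficacy subgroups (SAP 4.8) and the age criteria (Protocol 6.1) do not use this derived GA.

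It is also fair to say that a subtraction in days needs CGA captured in weeks and days, which the documents do not confirm.

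**Conclusion.** The derivation is wrong as written and should be corrected, though its reach is limited. On the plain reading, where CGA is used exactly or in completed weeks and only PNA is rounded up, GA is understated by up to 1.00 or 1.86 weeks respectively. In both cases 91 of 196 week-37 combinations are reported as preterm, 28 of them among the 49 at PNA 0 to 6 days. These counts give equal weight to every birth day and enrollment day. If CGA is rounded to the nearest week, errors run both ways; if it is rounded up, they largely reverse.

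The confirmed consequence is a biased GA summary and preterm/term split in SAP 6.1. A possible further consequence, if the 3.3 value feeds SAP 12.2.4, is that some 38-week babies are judged against bilirubin limits 2 to 3 mg/dL lower than those listed for their true GA.

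**What to change.** In SAP 3.3, compute GA in days as CGA (weeks and days converted to days) minus PNA in days, divide by 7, and apply no rounding before the cut-offs. This gives zero error and no misclassification for every combination above. For the example, 261 - 2 = 259 days = 37w0d.

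If GA at birth is recorded, use it directly. That becomes necessary if CGA is held only in whole weeks, because subtracting completed PNA weeks from completed CGA weeks gives either the right completed GA or one week too many. Protocol 6.2 ties the liver-test upper limits to the subject's GA, so sites refer to GA, but the data-capture form must be checked to see whether it is collected for analysis.

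State that the same GA is used for the 37-week category in SAP 6.1 and the 38-week columns in SAP 12.2.4. The cost is one formula, a source statement in two places and a check of the captured fields. Eligibility and conduct do not change.

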3.4 Definition of Baseline values

In general, baseline value for safety will be defined as the latest value prior to the first dose of BRV infusion, unless otherwise noted for a specific type of data. For almost all variables, this will be the assessment made at the Baseline visit. If a Baseline measurement is missing, and a Screening value available, the Screening value will be utilized as Baseline instead. If a Baseline assessment of biometric parameters (length, weight, head circumference) is taken on the same day as first dose of BRV infusion and assessment time is not known, the latest value at Screening or Baseline visit before or on the date of first dose of BRV infusion will be utilized as Baseline value.

Both scheduled and unscheduled assessments are considered.

Baseline efficacy will be defined in the efficacy analysis section.

3.5 Protocol deviations

Important protocol deviations (IPD) are deviations from the protocol that could potentially have a meaningful impact on key PK, efficacy, or safety outcomes for an individual subject. The criteria for identifying important protocol deviations and the classification of IPDs will be documented in a protocol-defined specification document. To the extent feasible, rules for identifying IPDs will be defined without review of the data and without consideration of the frequency of occurrence of such deviations. Whenever possible, criteria for identifying IPDs will be implemented algorithmically to ensure consistency in the classification of IPDs across all subjects.

Important protocol deviations will be reviewed as part of the ongoing data cleaning process prior to database lock to confirm exclusion from the Pharmacokinetic Per-Protocol Set.

3.6 Analysis sets

3.6.1 Safety Set

The Safety Set (SS) will consist of all enrolled subjects who take at least 1 dose of BRV. All safety analyses will be performed on the SS for the Exploratory Cohort and the Confirmatory Cohort(s).

3.6.2 Full Analysis Set

The Full Analysis Set (FAS) will be used for the analysis of seizure data (efficacy) and will consist of all subjects in the SS who have a minimum of 2 hours of interpretable VEEG data from both the Baseline period and the first 3 hours of the post-Baseline period after initial BRV treatment.

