8.2.1.1 Baseline Period

The Baseline Period will be up to 1 hour immediately prior to the start of initial BRV infusion and depend on seizure activity:

- For subjects with intermittent ENS: at least 1 hour prior to entering the Evaluation Period
- For subjects in status epilepticus: up to 30 minutes prior to entering the Evaluation Period. At least 15 minutes of continuous seizures, or 50% of cumulative seizure activity during a 30-minute interval are to be confirmed on EEG before the administration of BRV can start.

As soon as subjects are considered to be in status epilepticus, steps required for the preparation of the initial BRV infusion can be initiated (eg, assignment of BRV kits through interactive IRT and the dilution of BRV solution for iv infusion), even if the required EEG recording is not completed by that time.

The occurrence of ENS during the Baseline Period must be confirmed either by the local or central VEEG reader prior to drug administration. Preferably, the central VEEG reader should confirm the required ENS. Video-EEGs that are acquired per standard of care prior to consenting and meet study-specific technical and quality requirements (eg, ability for immediate cloud-based central review) can be used as part of the Baseline assessment VEEG.

The following assessments will be performed during the Baseline Period:

- Verification of inclusion/exclusion criteria. Confirmation on VEEG of ≥ 2 minutes of cumulative ENS or ≥ 3 identifiable ENS within the up to 1 hour prior to entering the Evaluation Period (ENS is defined as a seizure lasting for at least 10 seconds on VEEG), despite treatment with one or more AEDs per SOC
- Demographic data
- Medical history (including Apgar score)
- Vital signs (blood pressure, heart rate, respiratory rate [including apneas], oxygen saturation [pulse oximetry], and body temperature)
- Physical and neurological examination (Sarnat scale for subjects with HIE; physical examination will include a check for the presence of skin rash and skin hypersensitivity)
- Length
- Body weight
- Head circumference (Baseline measurement should be taken within 7 days prior to drug administration, or at birth for subjects ≤ 7 days old)
- Primary cause of seizure (HIE, hemorrhage, or infarction; CNS malformations; CNS infections; undetermined causes)
- N-PASS and EEG parameters for the assessment of sedation
- Video-EEG
- Heart rate monitoring

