10.3 Seizure burden

Seizure burden is defined as the total minutes of ENS per hour. Seizure burden information will be recorded for the Confirmatory Cohorts via a continuous VEEG. Seizure burden at Baseline will be evaluated over a period of at least 1 hour (subjects with intermittent seizures) or up to 30 minutes (subjects in status epilepticus).

Electroencephalographic neonatal seizures are defined as EEG seizures occurring for at least 10 seconds.

Seizure counts/seizure burden will be based on data collected using continuous VEEG. The VEEG recording will be evaluated by the local physician or central reader to evaluate eligibility of the subject. The VEEG recordings will subsequently be confirmed and quantified by the central reader at the end of the study.

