2.3.2 Confirmatory Cohorts

For the Confirmatory Cohorts, enrollment will only start after the dosing of BRV is determined based on the PK findings of the Exploratory Cohort and an existing PK model from N01263. A total of at least 36 subjects without adequate seizure control after receiving one or more of the following AEDs prior to or at the time of enrollment: PB, MDZ, PHT, LEV (\leq 60mg/kg/day), or LDC (first-line, second-line, or subsequent treatment, which may have started prior to the subject's admission into the study site; dose and dosing regimen at the Investigator's discretion) will enter the Confirmatory Cohorts. The AED treatment can be continued if the subject is on a stable dose for at least 1 hour at the time the first BRV infusion is initiated.

Three consecutive Confirmatory Cohorts (n=12 each) are planned; each cohort must have at least 2 subjects undergoing hypothermia treatment. A PK and safety data review will be performed by the DMC after completion of each of the 3 Confirmatory Cohorts (12 subjects each), but no later than intervals of 6 months. During the PK and safety data review of data from the first and second Confirmatory Cohorts, the recruitment of subjects into subsequent cohorts will continue.

The study periods for the Confirmatory Cohorts are as follows:

- Screening Period: from signing and dating of the written ICF up to initiation of the first BRV dose.

The Screening Period starts up to 36 hours prior to the first administration of BRV. Phenobarbital, MDZ, PHT, LEV ($\leq 60\text{mg/kg/day}$), or LDC may have been administered prior to the subject's enrollment into the study and/or at a location other than the study site.
- Baseline Period (included in the Screening Period):
 - For subjects with **intermittent ENS**: at least 1 hour prior to entering the Evaluation Period.
 - For subjects in status epilepticus: up to 30 minutes prior to entering the Evaluation Period. At least 15 minutes of continuous seizures, or 50% of cumulative seizure activity during a 30-minute interval are to be confirmed on EEG before the administration of BRV can start.

As soon as subjects are considered to be in status epilepticus, steps required for the preparation of the initial BRV infusion can be initiated (eg, assignment of BRV kits through interactive response technology [IRT] and the dilution of BRV solution for iv infusion), even if the required EEG recording is not completed by that time.

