Status epilepticus in neonates for the purpose of this study is defined as follows: 15 minutes of continuous or cumulative electrographic or electroclinical seizure within 30 minutes

The occurrence of ENS during the Baseline Period must be confirmed either by the local or central VEEG reader prior to BRV administration. Preferably, the central VEEG reader should confirm the required ENS. Video-EEGs that are acquired per standard of care prior to consenting and meet study-specific technical and quality requirements (eg, ability for immediate cloud-based central review) can be used as part of the Baseline assessment VEEG.
- Evaluation Period (96 hours): The first administration of BRV marks the starting point of the Evaluation Period. All subjects will receive iv BRV. The BRV dose for subjects in the Confirmatory Cohorts will be determined based on the results of the PK analysis of the Exploratory Cohort (predicted to be approximately the BRV plasma concentrations in the same range as those observed at the highest recommended dose in older children and adults who receive BRV 200mg/day). If subjects do not benefit from BRV treatment after 96 hours of BRV administration, BRV administration will be stopped and replaced by another AED.

Following the first BRV infusion, 6 PK blood microsamples (60 $\mu\text{L}/\text{sample}$) will be collected during the 96-hour Evaluation Period for each subject for the determination of plasma concentrations of BRV and its metabolites.

The AED PK sample should be collected 3 hours after the start of the initial BRV administration. In addition, opportunistic blood samples for the PK analysis may be used at the Investigator's discretion at any time during the Evaluation Period.

At the end of the Evaluation Period, subjects who benefit from BRV treatment may enter the BRV Extension Period in accordance with the Investigator's opinion. Subjects not entering the BRV Extension Period will proceed to the Down-Titration Period.

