3.2.2.2.2 Baseline Period

Baseline Period (-1h to 0h) begins 1 hour before and ends immediately prior to the first initiation of BRV infusion. The Baseline Period is included in the Screening Period.

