8.1.2 Baseline seizure burden

Baseline seizure burden is defined as seizure burden measured on the continuous VEEG (total ENS in minutes per hour) during a period of up to 1 hour immediately prior to the first administration of study medication.

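### The Full Analysis Set asks for 2 hours of VEEG from both periods, which does not fit a Baseline of 1 hour or up to 30 minutes, and no text says how to resolve this

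*SAP*

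**What the plan says.** SAP 3.6.2 builds the FAS from Safety Set (SS) subjects who have "a minimum of 2 hours of interpretable VEEG data from both the Baseline period and the first 3 hours of the post-Baseline period". Protocol 13.1 uses the same wording. SAP 4.6 and SAP 8 confine efficacy to FAS subjects of the Confirmatory Cohorts, and SAP 8.2.1 makes that set the denominator of the main secondary efficacy variable.

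The length of Baseline is stated in several places:

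- SAP 3.2.2.2.2: "Baseline Period (-1h to 0h) begins 1 hour before and ends immediately prior to the first initiation of BRV infusion".
- SAP 8.1.2: Baseline burden is measured "during a period of up to 1 hour immediately prior to the first administration of study medication".
- Protocol 8.2.1.1 opens with "The Baseline Period will be up to 1 hour immediately prior to the start of initial BRV infusion", but its first bullet reads "For subjects with intermittent ENS: at least 1 hour prior to entering the Evaluation Period". Protocol 5.1.2, Protocol 10.3, Table 5-2 footnote b and SAP 2.3.2 also give one hour as a minimum for these neonates. Footnote b to Protocol Figure 5-4 gives simply one hour.
- SAP 2.3.2: "For subjects in status epilepticus: up to 30 minutes prior to entering the Evaluation Period". The protocol agrees.

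Response is judged over the 2 hours that begin 1 hour after BRV starts (SAP 8.1.1). SAP Table 3.1 lists one departure from the protocol's analyses, on seizure-cause subgroups, and nothing on the FAS.

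**The concern.** The entry rule for the efficacy set appears to ask for more Baseline recording than the Baseline Period contains. Two ambiguities combine. The 2 hours may be required in each period or pooled over the two, and Baseline for intermittent seizures is described both as a maximum and as a minimum of one hour. A programmer cannot derive the FAS flag without settling both, and neither document does so.

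The FAS is the denominator of the main responder rate and of most other efficacy proportions, so the choice decides who is counted. Protocol 13.5.1 also judges efficacy by comparing the 95% CI of that responder rate with historical rates, although the SAP does not carry this rule over.

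As context only, the amendment log (Protocol 17.5) records that Baseline was shortened from 2 hours, so the 2-hour figure is probably a carry-over. The mismatch itself lies entirely within current text.

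**Working it through.** **Planned number.** Three Confirmatory Cohorts of 12 give 3 × 12 = 36, and 6 + 36 = 42 in total, as SAP 2.4 states. There is no power calculation to reproduce.

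**Inputs, in minutes.** Required: 120 (SAP 3.6.2). Baseline maximum: 60 (SAP 3.2.2.2.2), or 30 in status epilepticus (SAP 2.3.2). Post-dose period: 180. Response window: 120, from minute 60 to minute 180 after BRV starts (SAP 8.1.1).

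**Reading A: per period, SAP Baseline.** 60 < 120 and 30 < 120. The post-dose part is attainable (180 ≥ 120) but the Baseline part is not, so 0 of 36 qualify, whatever the mix of seizure types.

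**Reading B: per period, no cap for intermittent seizures.** Neonates with a status Baseline still fail (30 < 120). If s neonates have a status Baseline, at most 36 − s can qualify. The documents do not give s. For assumed values of 0, 12, 24 and 36 the ceiling is 36, 24, 12 and 0. The count actually reached also depends on how many of the others have 2 hours of pre-dose VEEG, which is not given either.

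**Reading C: pooled.** At most 60 + 180 = 240 or 30 + 180 = 210 minutes are available, both above 120, so all 36 could qualify. Suppose the Baseline is fully interpretable. The hour after BRV starts, before the response window opens, can absorb 60 of the post-dose minutes required:

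| Baseline | Post-dose minutes needed | Guaranteed in the response window |
|---|---|---|
| 60 | 120 − 60 = 60 | 60 − 60 = 0 of 120 |
| 30 | 120 − 30 = 90 | 90 − 60 = 30 of 120 |

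In the other direction, 120 post-dose minutes alone would satisfy the pooled rule. It therefore demands no Baseline VEEG at all, and without Baseline the percent change in SAP 8.1.5 cannot be computed.

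**A separate post-dose rule.** With 120 of the first 180 minutes required, at most 60 can fall before the window, so at least 120 − 60 = 60 of its 120 minutes are guaranteed.

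**Related divisor.** SAP 8.2.4 divides the Baseline total by 1 for the 96-hour burden reductions and for ENS frequency. For a total E recorded over 30 minutes, the hourly rate is E / 0.5 = 2E, but E / 1 = E. The Baseline rate is halved.

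**The case against.** The strongest reply is that zero depends on two choices together: the per-period reading and the one-hour cap. That is correct. Protocol 8.2.1.1 and SAP 2.3.2 also allow standard-of-care VEEG recorded before consent to count towards Baseline, so longer pre-dose recordings are foreseen. But minutes earlier than one hour before dosing lie outside the SAP's Baseline Period, and no such allowance rescues a neonate whose Baseline is at most 30 minutes.

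A second reply is that the sponsor would adopt a workable reading, that efficacy is descriptive with no tests (SAP 4.5), and that a blinded central reader quantifies the VEEGs at the end of the study (Protocol 5.1 and 10.3). This limits the consequences. A reader might infer that the rule will be chosen with results in view. Nothing in the documents indicates this, and the text can be settled before the central readings exist. It still has to be settled.

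Two stronger inferences are tempting and are not supported:

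- **Loss of the severe stratum under reading B.** Severe burden means more than 15 minutes of seizure in a 30-minute period (SAP 8.1.2.2), which also meets the status definition of "15 minutes of continuous or cumulative electrographic or electroclinical seizure within 30 minutes". A reader might conclude that nearly all severe neonates would be excluded. The number is not known. Entry may rest on the local reader (Protocol 5.1.2) while the analysis rests on the central reader alone (Protocol 13.5). The SAP's own example of a severe neonate has seizures in the second half-hour of Baseline, so severe neonates with longer Baselines are expected.
- **Responders turned into non-responders by the divisor.** The explicit division by 1 in SAP 8.2.4 belongs to variables that do not define response. The responder rule is in SAP 8.1.5, and SAP 8.1.4 divides by the hours in the period. SAP 8.1.5 does describe Baseline as one hour long, so its wording should be tidied, but a reversal of response status does not follow from SAP 8.2.4.

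**Conclusion.** The concern holds: the FAS criterion does not fit the current Baseline, and no passage reconciles them. The size depends on the reading:

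- Per period with the SAP's one-hour Baseline, 0 of at least 36 Confirmatory neonates qualify. This is what the text implies, not a forecast that nobody would be analysed.
- Per period without the cap, an unknown number qualify, and none with a status Baseline of up to 30 minutes.
- Pooled, the set is attainable but has no separate Baseline floor and secures only 0 or 30 minutes of the response window.

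The only efficacy set therefore cannot be programmed as written without an unstated choice, and this must be corrected. The scope is limited: efficacy is a secondary, descriptive objective, and the primary PK objective does not use the FAS. On safety, the documents support only one remark: SAP 10.4.9 names the FAS as the denominator for mechanical ventilation but presents the table for the SS, and the two statements must be reconciled.

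**What to change.** Before database lock, amend SAP 3.6.2, record the departure in SAP Table 3.1, and align Protocol 13.1 if the protocol is amended. Replace the single criterion with two separate minima:

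1. **Baseline.** A floor by seizure type that the defined Baseline can meet, fixed in advance by the sponsor. One example is at least 30 minutes of interpretable VEEG within the hour before the first BRV dose for intermittent seizures, and at least 15 minutes for status epilepticus. The second figure is attainable because Protocol Table 5-2 footnote b allows entry once 15 minutes of continuous seizure are confirmed. These are analysis floors only and leave study entry and the timing of treatment as they are.
2. **Post-dose.** At least 2 hours of interpretable VEEG within the first 3 hours after BRV starts.

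State which pre-dose minutes count as Baseline in the analysis, so that the one-hour minimum and the one-hour maximum for intermittent seizures no longer conflict.

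As a separate, minor conforming edit, SAP 8.2.4 should divide the Baseline total by the actual Baseline length, and SAP 8.1.5 should say the same instead of assuming one hour. In SAP 10.4.9, name one analysis set.

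The cost is a SAP amendment: wording only, with no new data and no change to conduct.
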